## Protocol Synopsis

**Title:** A Phase I, Randomized, Open-label Multiple-dose Study to Evaluate Safety, Tolerability, and Pharmacokinetics of AMG 334 in Children and Adolescents with Migraine

**Study Phase:** 1b

**Indication:** Migraine prevention

**Primary Objectives:** To evaluate the safety, tolerability, and pharmacokinetic (PK) profile following multiple subcutaneous (SC) doses of AMG 334 in children and adolescent subjects with migraine, respectively.

**Exploratory Objectives:**

**Hypotheses:** Multiple SC doses of AMG 334 will be safe and well-tolerated, and the PK profiles will support further development of AMG 334 in children and adolescents with migraine, respectively.

**Primary Endpoints:**

- Serum PK parameters of AMG 334 (eg, time to maximum concentration [ $t_{max}$ ]), maximum observed concentration [ $C_{max}$ ], trough concentration ( $C_{trough}$ ), area under the concentration time curve (AUC) from 0 to 28 days ( $AUC_{0-28day}$ )
- Treatment-emergent adverse events
- Changes in vital signs, 12-lead electrocardiograms (ECGs), clinical laboratory safety tests, and neurological assessments

**Exploratory Endpoints:**

**Study Design:**

This is a Phase 1b multicenter, randomized, open-label, multiple-dose study evaluating AMG 334 in male and female children (6 to < 12 years of age) and adolescents (12 to < 18 years of age) with migraine. The study population will consist of 2 cohorts based on body weight enrolling a total of at least **52** subjects and up to approximately 60 subjects in the study. Cohort 1 will enroll at least **12** subjects and up to approximately 22 subjects in total with body weight of < 40 kg. At least **9** subjects in Cohort 1 must be aged 6 to < 12 years including at least **2** subjects aged 6 to < 10 years, at the time of consent. Cohort 2 will enroll at least 35 subjects and up to approximately 38 subjects in total with a body weight of  $\geq 40$  kg at baseline. It is anticipated that most subjects in this cohort will be 12 to < 18 years of age. Enrollment requirements for subjects in Cohort 1 and Cohort 2 will be tracked and administered via IVRS to ensure that the minimum number of subjects in each cohort is achieved.

Enrollment will be staggered by age category with adolescents (ie, subjects 12 to < 18 years of age) starting enrollment first.

Children 6 to < 12 years of age at the time of consent will participate in the initial treatment phase for a total of 12 weeks of treatment. Adolescents 12 to < 18 years of age at time of consent will participate in the initial treatment phase for a total of 12 weeks of treatment after which they will have the option of continuing treatment in an optional 40-week extension phase, for a total of 52 weeks of treatment. A safety follow-up visit will take place 16 weeks after the last dose to complete end of study (EOS) assessments either (i) after completion of the initial 12 week treatment phase, (ii) after completion of the optional 40-week extension phase for those adolescents who choose to continue treatment, or (iii) after the last dose received before discontinuation of treatment during the study.

Subjects weighing < 40 kg (Cohort 1) will receive a dose of either 35 mg or 70 mg for a total of at least **12** and up to approximately **15** subjects completing Week 12 assessments. Subjects weighing  $\geq 40$  kg (Cohort 2) will receive a dose of either 70 mg or 140 mg for a total of at least 26 and up to approximately 30 subjects completing Week 12 assessments. Treatments will be allocated to qualifying subjects in a randomized order within either cohort through IVRS. Study drug (low-dose or high-dose AMG 334) will be administered in either cohort in an open-label fashion against a background of allowed concomitant medications, including agents for migraine prevention.

It is anticipated that at least **52** and up to approximately 60 subjects will be enrolled in the study to ensure that at least **38** and up to approximately **45** subjects complete Week 12 assessments.

During the initial treatment phase, each subject will receive a total of 3 SC doses of AMG 334 administered every 4 weeks (Q4W) as described in the Schedule of Activities ([Table 1](#) and [Table 2](#)). The study is expected to confirm a PK profile in pediatric subjects that is similar to that in adults, based on population PK analysis, and to provide preliminary safety data in each body-weight cohort supportive of the initiation of the AMG 334 Phase 3 studies in the pediatric population.

All subjects will be administered AMG 334 against a background of allowed concomitant medications, including agents for migraine prevention (up to 2 treatments on a stable dose) and for acute treatment of migraine.

#### **Sample Size:**

A total of at least **52** subjects and up to approximately 60 subjects with migraine will be enrolled in Cohorts 1 and 2. The rate of early discontinuation up to Week 12 assessments is assumed to be 20% and similar across the two cohorts. In Cohort 1, (< 40 kg), at least **12** subjects and up to approximately 22 subjects will be enrolled in order to have at least **12** and up to approximately **15** subjects completing Week 12 assessments. In Cohort 2, ( $\geq 40$  kg), at least 35 subjects and up to approximately 38 subjects will be enrolled in order to have at least 26 and up to approximately 30 subjects completing Week 12 assessments. All subjects in this study will be administered AMG 334. The sample size for this study is based on clinical and practical considerations to adequately fulfil its objectives and to inform planned Phase 3 pediatric studies. Assuming clearance (CL) and central volume of distribution (Vc) on mg/kg basis are similar between pediatric and adult subjects, and assuming percent coefficients of variation (%CV) for CL and Vc are 43% and 53%, respectively, (based on total between-subject-variability from adult population PK), the proposed sample size provides > 80% power to estimate 95% confidence interval (CI) of CL and Vc within 60-140% of the true parameters for both weight cohorts combined and across the two age categories.

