Subjects weighing < 40 kg (Cohort 1) will receive a dose of either 35 mg or 70 mg for a total of at least **12** and up to approximately **15** subjects completing Week 12 assessments. Subjects weighing  $\geq$  40 kg (Cohort 2) will receive a dose of either 70 mg or 140 mg for a total of at least 26 and up to approximately 30 subjects completing Week 12 assessments. Treatments will be allocated to qualifying subjects in a

randomized order within either cohort through IVRS. Study drug (low-dose or high-dose AMG 334) will be administered in either cohort in an open-label fashion against a background of allowed concomitant medications, including agents for migraine prevention.

It is anticipated that at least **52** and up to approximately 60 subjects will be enrolled in the study to ensure that at least **38** and up to approximately **45** subjects complete Week 12 assessments.

During the initial treatment phase, each subject will receive a total of 3 SC doses of AMG 334 administered every 4 weeks (Q4W) as described in the Schedule of Activities ([Table 1](#) and [Table 2](#)). The study is expected to confirm a PK profile in pediatric subjects that is similar to that in adults, based on population PK analysis, and to provide preliminary safety data in each body weight cohort supportive of the initiation of the AMG 334 Phase 3 studies in the pediatric population. All subjects will be administered AMG 334. Concomitant use of agents for migraine prevention (up to 2 treatments on a stable dose) and for the acute treatment of migraine are permitted during the study.

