### **3.3 Number of Subjects**

Participants in this clinical investigation shall be referred to as “subjects”.

A total of at least **52** subjects and up to approximately 60 subjects with migraine will be enrolled in Cohorts 1 and 2, with at least **12** subjects and up to approximately 22 subjects enrolled into Cohort 1 (< 40 kg) and at least 35 subjects and up to approximately 38 subjects enrolled into Cohort 2 ( $\geq 40$  kg). The number of subjects enrolled into Cohort 1 and Cohort 2 are considered sufficient in order to collect appropriate PK data and preliminary safety data able to support the initiation of the AMG 334 pediatric Phase 3 safety and efficacy studies. This includes an anticipated rate of early discontinuations up to 20% over the first 12 weeks, which is expected to be similar across the two cohorts.

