### **3.4 Replacement of Subjects**

Subjects who are withdrawn or removed from treatment or the study may be replaced by another subject in the same body weight cohort at the discretion of the Amgen Medical Monitor in consultation with the Principal Investigator.

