**10.2 Sample Size Considerations**

The study population will consist of 2 cohorts based on body weight enrolling a total of at least **52** subjects up to approximately 60 subjects in the study. Cohort 1 will enroll at least **12** subjects and up to approximately 22 subjects with body weight of < 40 kg at baseline. It is anticipated that most subjects in this cohort will be 6 to < 12 years of age. Cohort 2 will enroll at least 35 subjects and up to approximately 38 subjects with a body weight of  $\geq 40$  kg at baseline. It is anticipated that most subjects in this cohort will be 12 to < 18 years of age.

Subjects weighing < 40 kg (Cohort 1) will receive a dose of 35 mg or 70 mg for a total of at least **12** and up to approximately **15** subjects completing Week 12 assessments.

Subjects weighing  $\geq 40$  kg (Cohort 2) will receive a dose of 70 mg or 140 mg for a total of at least 26 and up to approximately 30 subjects completing Week 12 assessments.

The rate of early discontinuation up to Week 12 assessments is assumed to be 20% and similar across the two cohorts.

All subjects in this study will be administered AMG 334. The sample size for this study is based on clinical and practical considerations to adequately fulfil its objectives and to inform on planned phase 3 pediatric studies. Assuming clearance (CL) and central volume of distribution (Vc) on mg/kg basis is similar between pediatric subjects and adults, and assuming %CV for CL and Vc are 43% and 53%, respectively, (based on total between-subject-variability from adult population PK), the proposed sample size provides > 80% power to estimate 95% CI of CL and Vc within 60-140% of the true

parameters for both weight cohorts combined and across the two age categories (Wang Y et al, 2012).

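### Cohort 1 pairs a minimum of 12 enrolled with a minimum of 12 Week 12 completers, which leaves no room for the 20% dropout the plan assumes

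*Protocol*

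**What the plan says.** The Synopsis sample size paragraph gives Cohort 1 a minimum enrolment of 12, "subjects and up to approximately 22 subjects will be enrolled in order to have at least" 12 and up to about 15 completing Week 12. For Cohort 2 it says "at least 35 subjects and up to approximately 38 subjects will be enrolled in order to have at least 26 and up to approximately 30" completing Week 12.

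The dropout assumption is in the same Synopsis paragraph, in Protocol 10.2 and in SAP 3.2: "The rate of early discontinuation up to Week 12 assessments is assumed to be 20% and similar across the two cohorts". All three places carry the Cohort 1 enrolment minimum of 12, the completer minimum of 12 and the 20%. Protocol 3.1 and SAP 3.1 give the 12 and 12 without the rate.

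Protocol 3.3 gives the enrolment ranges by cohort, calls them sufficient, and adds: "This includes an anticipated rate of early discontinuations up to 20% over the first 12 weeks". It states no completer target.

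For the study as a whole, Protocol 3.1 says that at least 52 "and up to approximately 60 subjects will be enrolled in the study to ensure that at least" 38 and up to about 45 complete Week 12. Under Protocol 3.4, subjects who are withdrawn "may be replaced by another subject in the same body weight cohort", at the discretion of the medical monitor in consultation with the investigator.

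**The concern.** The Synopsis presents enrolment as the means of reaching the completer count. An enrolment minimum equal to the completer minimum works only if nobody drops out, yet the sentence before it assumes that one in five will. Section 3.3 then says the enrolment numbers already include dropout of up to 20%. Set against the completer target stated elsewhere, that is not so for the Cohort 1 minimum.

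Cohort 1 is the smaller cohort and is expected to be mostly children aged 6 to under 12. It is split 1:2 between two doses, and PK and safety are to be summarised by cohort and dose. At 12 enrolled the split is 4 and 8; after a 20% loss about 3.2 and 6.4 would complete. Someone planning from these documents could take 12 enrolled as enough for 12 complete Week 12 profiles below 40 kg.

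**Working it through.** **Inputs.** Enrolment and completer figures and the 20% rate: Protocol Synopsis, 3.1 and 10.2; SAP 3.1 and 3.2. The rate is applied as 20% in each cohort, as the documents state.

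**Step 1: test each stated pair.** Implied loss = 1 − completers / enrolled. Enrolment needed at 20% loss = completers / 0.8, rounded up. Expected completers = enrolled × 0.8.

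| Pair | Enrolled | Completers | Implied loss | Needed at 20% | Expected completers |
|---|---|---|---|---|---|
| Cohort 1, lower | 12 | 12 | 0% | 15 | 9.6 |
| Cohort 1, upper | 22 | 15 | 31.8% | 19 | 17.6 |
| Cohort 2, lower | 35 | 26 | 25.7% | 33 | 28.0 |
| Cohort 2, upper | 38 | 30 | 21.1% | 38 | 30.4 |
| Total, lower | 52 | 38 | 26.9% | 48 | 41.6 |
| Total, upper | 60 | 45 | 25.0% | 57 | 48.0 |

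The Cohort 2 figures follow from the 20% rate exactly (38) or closely (33 against 35). The remaining pairs, apart from the Cohort 1 minimum, enrol more than the rate requires. The Cohort 1 minimum is the only one that falls short, by 15 − 12 = 3 subjects.

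**Step 2: the smallest Cohort 1 the total allows.** The cohort minima sum to 12 + 35 = 47, below 52. With Cohort 2 at its upper figure, 12 + 38 = 50, so a total of 52 needs 52 − 38 = 14 in Cohort 1. With Cohort 2 at its minimum it needs 52 − 35 = 17. The minima are therefore compatible with 52, but 12 is not the number that operates in practice.

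**Step 3: chance of at least 12 completers in Cohort 1.** This uses the exact binomial, assuming independent dropout, with completion probability 0.8.

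| Enrolled in Cohort 1 | Expected completers | P(at least 12) |
|---|---|---|
| 12 | 9.6 | 0.8^12 = 6.9% |
| 14 | 11.2 | 44.8% |
| 15 | 12.0 | 64.8% |
| 16 | 12.8 | 79.8% |
| 17 | 13.6 | 89.4% |

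**Step 4: lower dropout.** Section 3.3 gives 20% as an upper limit, so smaller rates were also tried.
- 10% loss: 12 enrolled gives 10.8 expected and 28.2%; 14 enrolled gives 12.6 and 84.2%.
- 5% loss: 12 enrolled gives 11.4 expected and 54.0%.

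**Step 5: what is not affected.**
- At 20% loss, 52 enrolled gives 41.6 expected completers and P(at least 38) = 91.8%.
- Cohort 2 at 35 gives 28.0 expected and P(at least 26) = 85.4%.
- The precision statement (CV 43% for clearance, 53% for central volume, interval within 60–140% of the true value, power above 80%) is for both cohorts combined. Assuming log-normal parameters, 38 completers give about 0.998 for clearance and 0.98 for volume.

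**The case against.** The strongest defence is that these are two ranges, not a calculated pair. Both ends carry an at-least or an up-to-approximately. Enrolling 12 to 22 at 20% loss yields about 9.6 to 17.6 completers, which spans the 12 to 15 wanted. On that reading the plan sets two separate floors, and enrolment simply continues, or withdrawals are replaced under 3.4, until 12 have completed. The total of 52 also pushes Cohort 1 above 12.

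Part of this stands. There are routes to 12 completers, and 12 enrolled is not where the cohort would end. It does not rescue the figure. The Synopsis ties the two floors together as means and end. Replacement is discretionary, is not mentioned in 10.2 or SAP 3.2, and each replacement is a further enrolment. At 14, the lowest the total allows with Cohort 2 at about 38, the expected number is still below 12.

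Four further points are fair:
- The upper figure for Cohort 2 is approximate, so 14 is approximate too.
- The probabilities treat enrolment as starting from nothing. SAP Section 10 records that at least 8 children had completed Week 12 by May 2021, before the amendment of 3 November 2021. Their weight cohort is not given, so the probabilities cannot be updated.
- The plan sets no target probability of reaching 12.
- No analysis is triggered by or depends on 12 Cohort 1 completers. The second interim analysis is triggered by 8 children, the safety set needs one dose, and the PK set needs one dose and one concentration result.

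These points limit the consequence. They do not make the arithmetic consistent.

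**Conclusion.** The concern holds. The Cohort 1 minimum pair allows 0% dropout where the plan assumes 20%. The plan's own rate gives about 10 completers from 12 enrolled, or about 11 from the 14 that the total of 52 requires with Cohort 2 at about 38. The conclusion rests on the 20% rate applying to Cohort 1, as the documents say. At 10% loss, 12 enrolled still falls short on expectation (10.8), while 14 would be enough (12.6).

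The practical effect is modest. The overall 38 completers, the Cohort 2 figures, the combined precision statement and the descriptive analyses are all unaffected. What fails is a stated sample size figure, repeated in both documents, and it should be corrected.

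**What to change.** Make one change, consistently, in the Synopsis, Protocol 3.1 and 10.2, and SAP 3.1 and 3.2. Section 3.3 gives no completer count and needs only a matching edit to its statement about included dropout.

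- **Wording only (sufficient).** Keep the enrolment minimum and state the completers it implies: about 9 to 10 at 12 enrolled, or about 11 at the 14 implied by the total of 52. Add that the overall 38 completers rests on enrolling 52, not on 12 + 26. If replacement under 3.4 is what secures 12 completers, 10.2 and SAP 3.2 could keep the target and say so. The cost is either a slightly less favourable completer figure or an explicit reliance on replacement. The Amendment 5 rationale lists 52 enrolled and at least 12 below 40 kg but no Cohort 1 completer count, so it is not touched.
- **Raise the stated minimum (optional).** Keep at least 12 completers and state a matching enrolment. Fifteen is the bare 20% figure (12.0 expected, 65% chance) and needs Cohort 2 at 37 to reach 52. Seventeen reaches 52 with Cohort 2 at 35 (13.6 expected, 89% chance). Both fit within the upper figures of 22, 38 and 60. The cost is a stated minimum 1 to 3 above the 14 already implied.

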### **Summary of Subject Eligibility Criteria:**

Male and female subjects ages 6 to < 18 years with a history of migraines at least twelve months prior to screening and with a frequency of  $\geq 4$  migraine days per month for three months prior to screening. For a full list of eligibility criteria, please refer to Section 4.1 and Section 4.2.

It is anticipated that at least **52** and up to approximately 60 subjects in total will be enrolled in the study to ensure that at least **38** and up to approximately **45** subjects complete Week 12 assessments.

### **Investigational Product**

#### **Amgen Investigational Product Dosage and Administration:**

Investigational product (IP) (ie, AMG 334) will be dosed subcutaneously. Doses are fixed, based on body weight taken at Day 1, and must not be adjusted for individual subjects during the study; eg due to changes in body weight. Subjects weighing < 40 kg (Cohort 1) will receive a dose of either 35 mg or 70 mg. Subjects weighing  $\geq 40$  kg (Cohort 2) will receive a dose of either 70 mg or 140 mg.

AMG 334 will be packaged as 70 mg/mL in 1 mL or 140 mg/mL in 1 mL pre-filled syringes and 70 mg/mL vials. Subjects in Cohort 1 (weighing < 40 kg) will be randomized in a 1:2 allocation ratio to low dose (35 mg AMG 334) or high dose (70 mg AMG 334). Subjects in Cohort 2 (weighing  $\geq 40$  kg) will be randomized in a 1:4 allocation ratio to low dose (70 mg AMG 334), or high dose (140 mg AMG 334). The anatomical sites for administration of Investigational Product are the upper arm, upper thigh, or abdomen.

### **Procedures:**

After written informed consent and assent are obtained, all screening tests and procedures will be performed within 21 days before the administration of the first dose of AMG 334 (Study Day 1), unless otherwise noted.

Following the first AMG 334 dose administration on Day 1, all subjects will be monitored at the facility for at least 2 hours post-dose, at which point they will be discharged with instructions to return to the research facility according to the procedures provided in the Schedule of Activities ([Table 1](#) and [Table 2](#)). At the 12 Week visit, adolescent subjects may choose to continue onto the optional 40-week extension phase. All subjects will be followed for 16 weeks after the last administration of AMG 334.

Blood samples for PK, [REDACTED], clinical laboratory safety assessments, and pharmacogenomic assessments will be collected. Vital signs, physical examinations, and ECGs will be performed at predetermined time points throughout the study. All adverse events and use of concomitant medications will be collected for the duration of the study, up to and including the EOS visit. All treatment-emergent adverse events or laboratory abnormalities will be followed until resolution of the abnormality or until it is considered stable in the opinion of the investigator.

For a full list of study procedures, including the timing of each procedure, please refer to Section 7 and the Schedule of Activities ([Table 1](#) and [Table 2](#)).

### **Statistical Considerations:**

Descriptive statistics will be provided for selected demographic, safety, and PK data. Descriptive statistics on continuous measurements will include means, medians, standard deviations, first quartile (Q1), third quartile (Q3), minimum, and maximum, while categorical data will be summarized using frequency counts and percentages. For a full description of statistical analysis methods, please refer to Section 10.

---

The primary analysis of the safety and PK data will occur after all subjects in both body weight cohorts have completed the initial 12 Week treatment phase (ie, Week 12 assessments). No formal hypothesis testing will be performed; all analyses will be descriptive. PK and safety data will include summaries by body weight cohort and AMG 334 treatment dosage group. The review of the results of this primary analysis will inform further pediatric studies utilizing AMG 334.

There are 2 interim analyses of PK and safety planned for this study. The first interim analysis will occur when at least 6 adolescents (12 to < 18 years of age) have completed study Week 8 assessments. The second interim analysis will occur when at least **8** children (6 to < 12 years of age) have completed study Week 12 assessments. For both interim analyses, PK data, adverse events, vital sign data, and laboratory data will be summarized. The purpose of the first and second interim analysis is to inform the selection of AMG 334 doses to be evaluated in the Phase 3 pediatric AMG 334 studies. The final safety analysis for the study will be performed at the end of the trial, including the 40-week extension phase and the safety follow-up. No formal hypothesis testing will be performed; all analyses will be descriptive.

[figure not shown]
---

**Sponsor:** Amgen Inc.

